Visit and Visit Window	Screening/ Baseline ^a	2 year ^b ± 2 months	4 year ^b ± 2 months ^c	Prior to DME/PDR Treatment Initiation ^d
Best corrected visual acuity	X	X	X	X
Eye Exam ^{e, f}	X	X	X	X
DRCR.net Fundus Photography ^{e, g}	X	X	X	X
Spectral Domain OCT ^e	X	X	X	X
Collection of Adverse Events occurring during the visit	X	X	X	X

249 a. To be performed within 3 months of the PROMINENT randomization visit

250 b. Time from randomization into the PROMINENT trial.

- 251 c. If the PROMINENT trial ends before a participant reaches the 4 year visit, one final visit within 3 months of
252 the PROMINENT trial ending will be completed.
- 253 d. All study procedures should be performed prior to the initiation of treatment for DME or DR in a study eye.
- 254 e. After pupil dilation
- 255 f. Participants may opt out of eye exam particularly if they have recently had an eye exam
- 256 g. The widest camera type available will be used for color fundus photography.

257
258 **F. Outcomes**

259 Primary outcome:

260
261 The primary outcome is diabetic retinopathy worsening or DME development (composite outcome),
262 based on both eyes for bilateral participants and based on the study eye only for unilateral
263 participants. Study eye is defined based on the criteria in section 2.2.2 as the eye(s) having ETDRS
264 Diabetic Retinopathy Severity level between 20 and 53 (minimal to severe NPDR), inclusive,
265 according to the investigator and confirmed by central Reading Center, without definite central
266 subfield involved diabetic macular edema.

267
268 Diabetic retinopathy worsening or DME development is defined as any of the following:

- 269
- 270 • For participants with 2 study eyes: 3-step worsening on the ETDRS Retinopathy Severity Scale
271 for Persons (Table 1 in Section 6) at a protocol visit. This scale takes into account the
272 retinopathy level of both study eyes.
 - 273 • For participants with one study eye: 2-step worsening on the ETDRS Retinopathy Severity
274 Scale for Individual Eyes (Table 2 in Section 6) in the study eye at a protocol visit. This scale
275 only takes into account the retinopathy level of the study eye.
 - 276 • Procedure undertaken for the treatment of PDR at any time (even in the absence of photographic
277 documentation) including PRP, intravitreal anti-VEGF, or vitrectomy in at least one study eye.
 - 278 • Treatment initiated for DME at any time (even in the absence of OCT documentation) including

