279 anti-VEGF, corticosteroids, focal/grid laser, or vitrectomy in at least one study eye.
 - 280 • Development of central-involved DME on OCT with vision loss at the 2-year or 4-year visit.
281 Defined as OCT central subfield thickness above the machine and gender-specific thresholds
282 (see Section 2.2.2 for details) with at least a 10% increase in thickness from baseline and visual
283 acuity 20/32 or worse (letter score ≤ 78) in at least one study eye.
- 284

285 Secondary outcomes include a treatment comparison of the following:

286
287 Participant-Level Secondary Outcomes (relates to either eye for bilateral participants and to the
288 study eye for unilateral participants):

- 289
- 290 • Hazard rate of 3-step person-level (for bilateral participants, see Table 1 in Section 6) or 2-step
291 eye-level (for unilateral participants, see Table 2 in Section 6) diabetic retinopathy worsening on
292 the ETDRS Retinopathy Severity Scale or receiving treatment for PDR in at least one study eye
293 at any time (irrespective of DME status or treatment)
 - 294 • Hazard rate of developing central-involved DME on OCT with vision loss (as defined above) or
295 receiving treatment for DME in at least one study eye at any time (irrespective of diabetic
296 retinopathy severity level or treatment)
 - 297 • Person-level diabetic retinopathy severity at 2 years and 4 years
 - 298 • Percentage of participants with at least a 2-line loss in visual acuity from baseline in at least one
299 study eye at 2 years and 4 years

300
301
302
303
304
305
306
307
308
309
310
311
312
313
314
315
316
317
318
319
320
321
322
323
324
325
326
327
328
329
330
331
332
333
334
335
336
337
338
339
340
341
342
343
344

Eye-Level Secondary Outcomes (evaluated only for study eyes):

- Hazard rate of a composite PDR/DME outcome. Defined as the time to 2-step diabetic retinopathy worsening on the ETDRS Retinopathy Severity Scale for Individual Eyes (see Table 2 in Section 6) at 2 years or 4 years, development of central-involved DME on OCT with vision loss (as defined above) at 2 years or 4 years, or treatment for DME or PDR at any time
- Hazard rate of 2-step diabetic retinopathy worsening or receiving treatment for PDR at any time (irrespective of DME status or treatment)
- Hazard rate of developing central-involved DME on OCT with vision loss at 2 years or 4 years or receiving treatment for DME at any time (irrespective of diabetic retinopathy level or treatment)

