3.1 Visit Schedule

Each participant will have protocol specific follow-up visits scheduled at 2 years (\pm 2 months) and at 4 years (\pm 2 months) from the randomization date in the PROMINENT trial. If the PROMINENT study ends prior to a participant's 4-year visit, the participant will have one closeout visit within 3 months of the last PROMINENT visit.

436 Additional retina evaluation visits may occur as required for usual care of the study participant
437 either by the DRCR.net clinical site or by the participant's non-DRCR.net ophthalmologist. If the
438 participant will be examined by a non-DRCR.net ophthalmologist, the participant will be asked to
439 sign a medical records release so any treatment that is documented can be obtained by the
440 DRCR.net site. In addition, participants for whom ocular treatment for DR or DME is planned for
441 the first time during the trial (e.g. anti-VEGF or corticosteroid intravitreal injection, PRP,
442 focal/grid laser, or vitrectomy) will be asked to return to the DRCR.net clinical site to complete the
443 study procedures before the treatment is administered, provided treatment is not urgently needed as
444 determined by the treating physician. If pre-treatment images are not able to be obtained, study
445 images should try to be obtained within 1 month after treatment initiation. Participants who receive
446 treatment will continue follow-up through 4 years.

447
448 Communication between the PROMINENT clinical site and the PROMINENT-Eye clinical site
449 may occur to facilitate compliance with the follow-up schedule if needed.

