5.3 Study Participant Withdrawal and Losses to Follow-up

A study participant has the right to withdraw from the study at any time. If a study participant is considering withdrawal from the study, the principal investigator should personally speak to the individual about the reasons, and every effort should be made to accommodate him or her.

The goal for the study is to have as few losses to follow-up as possible. The Coordinating Center will assist in the tracking of study participants who cannot be contacted by the site. The Coordinating Center will be responsible for classifying a study participant as lost to follow-up.

Study participants who withdraw will be asked to have a final closeout visit at which the testing described for the protocol visits will be performed.

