6.1 Primary Outcome

The primary outcome is diabetic retinopathy worsening or DME development (composite outcome), based on both eyes for bilateral participants and based on the study eye only for unilateral participants. From a statistical perspective, the primary outcome is a person-level outcome as data from both eyes of bilateral participants is combined into a single outcome measurement. The primary outcome is defined as any of the following:

- For participants with 2 study eyes: 3-step worsening on the ETDRS Retinopathy Severity Scale for Persons (**Table 1**) at a protocol visit. This scale takes into account the retinopathy level of both study eyes.
- For participants with one study eye: 2-step worsening on the ETDRS Retinopathy Severity Scale for Individual Eyes (**Table 2**) in the study eye at a protocol visit. This scale only takes into account the retinopathy level of the study eye.
- Procedure undertaken for the treatment of PDR at any time (even in the absence of photographic documentation) including PRP, intravitreal anti-VEGF, or vitrectomy in at least one study eye.
- Treatment initiated for DME at any time (even in the absence of OCT documentation) including anti-VEGF, corticosteroids, focal/grid laser, or vitrectomy in at least one study eye.
- Development of central-involved DME on OCT with vision loss at the 2-year or 4-year visit. Defined as OCT central subfield thickness above the machine and gender-specific thresholds (see Section 2.2.2 for details) with at least a 10% increase in thickness from baseline and visual acuity 20/32 or worse (letter score ≤ 78) in at least one study eye.

Table 1: Summary of ETDRS Final Retinopathy Severity Scale for Persons

Level in each eye	Description	Scale step
10/10	No DR	1
20/< 20	Microaneurysms only, one eye	2
20/20	Microaneurysms only, both eyes	3
35/< 35	Mild NPDR, one eye	4
35/35	Mild NPDR, both eyes	5
43/< 43	Moderate NPDR, one eye	6
43/43	Moderate NPDR, both eyes	7
47/< 47	Moderately severe NPDR, one eye	8
47/47	Moderately severe NPDR, both eyes	9
53/< 53	Severe or very severe NPDR, one eye	10
53/53	Severe or very severe NPDR, both eyes	11
60 or 61/< 60	Mild PDR and/or PRP, one eye	12
60 or 61/60 or 61	Mild PDR and/or PRP, both eyes	13
65/< 65	Moderate PDR, one eye	14
65/65	Moderate PDR, both eyes	15
71+/< 71	High-risk PDR, one eye	16
71+/71+	High-risk PDR, both eyes	17

587

588
589

Table 2: Summary of ETDRS Final Retinopathy Severity Scale for Individual Eyes

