 611 15% attrition over 4 years, also assumed to follow an exponential distribution.

612

Table 3. Required Number of Participants for Primary Analysis

Hazard Ratio	Placebo Event Rate				
	16%	14%	12%	10%	8%
0.30	270	310	364	438	552
0.40	398	458	536	646	812
0.50	618	710	832	1000	1256

613

614

615
616 The projected 4-year outcome rates of 5% in the pema fibrate group and 12% in the placebo group
617 yield a hazard ratio of approximately 0.4, resulting in a required sample size of 536 participants.
618

619 Assuming 600 participants are enrolled of whom 15% are lost to follow up over 4 years, the
620 detectable hazard ratio with 80% power is 0.49 for a placebo event rate of 16% to 0.32 for a placebo
621 event rate of 8%. In other words, the study is powered for a reduction in the rate of diabetic
622 retinopathy worsening by 1/2 to 2/3, depending on the event rate in the placebo group. The placebo
623 event rate could be higher than 16% because the 12% estimate from ACCORD accounts for events
624 due only to progression of retinopathy on photographs and does not include treatment-related and
625 DME-related events, which are other components of the composite outcome. There are no existing
626 data on which to base estimates for rates of these outcomes. In the event that the outcome rates in
627 the placebo group are higher than projected, the study will be powered to detect smaller reductions
628 in the hazard of diabetic retinopathy worsening. Therefore, the estimates given here are
629 conservative.
630

631 **6.3 Primary Analysis Plan**

632 **6.3.1 Principles for Analysis**

633 The primary treatment group comparison will be based on the hazard ratio from a Cox proportional
634 hazards regression model that adjusts for the baseline person-level retinopathy, which accounts for
635 the retinopathy level in the non-study eye of unilateral participants (see **Table 1**). The primary
636 analysis is an intention-to-treat analysis. Data from participants who are not observed to meet
637 outcome criteria and who are lost to follow up will be censored at the time of the last completed
638 visit. All model assumptions, including proportional hazards, will be verified. If model
639 assumptions are not reasonably satisfied, alternative approaches will be explored.
640

641 **6.3.2 Confounding**

642 Imbalances between groups in important covariates are not expected to be of sufficient magnitude

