715 compared similarly but without adjustment for inter-eye correlation.

716
717 All analyses will include adjustment for the baseline level of the outcome, where appropriate. In
718 addition, participant-level and eye-level secondary outcomes will be adjusted for baseline person-
719 level diabetic retinopathy severity. The treatment groups will be compared on the following
720 outcomes of interest:

721
722 Participant-Level Secondary Outcomes (relates to either eye for bilateral participants and to the
723 study eye for unilateral participants):

- 724
- 725 • Hazard rate of 3-step person-level (for bilateral participants, **Table 1**) or 2-step eye-level (for
726 unilateral participants, **Table 2**) diabetic retinopathy worsening on the ETDRS Retinopathy
727 Severity Scale or receiving treatment for PDR in at least one study eye at any time (irrespective
728 of DME status or treatment)
 - 729 ○ Percentage of participants with diabetic retinopathy worsening at 2 years and 4 years
730 will be enumerated without statistical comparison
 - 731 ○ Percentage of participants receiving treatment for PDR in at least one study eye at or
732 prior to 2 years and 4 years will be enumerated without statistical comparison
 - 733 • Hazard rate of developing central-involved DME on OCT with vision loss (as defined in Section
734 6.1) or receiving treatment for DME in at least one study eye at any time (irrespective of
735 diabetic retinopathy severity level or treatment)
 - 736 ○ Percentage of participants with central-involved DME on OCT with vision loss in at
737 least one study eye at 2 years and 4 years will be enumerated without statistical
738 comparison
 - 739 ○ Percentage of participants receiving treatment for DME in at least one study eye at or
740 prior to 2 years and 4 years will be enumerated without statistical comparison
 - 741 • Person-level diabetic retinopathy severity at 2 years and 4 years
 - 742 • Percentage of participants with at least a 2-line loss in visual acuity from baseline in at least one
743 study eye at 2 years and 4 years

744
745 Eye-Level Secondary Outcomes (evaluated only for study eyes):

- 746
- 747 • Hazard rate of a composite PDR/DME outcome. Defined as the time to 2-step diabetic
748 retinopathy worsening on the ETDRS Retinopathy Severity Scale for Individual Eyes
749 (**Table 2**) at 2 years or 4 years, development of central-involved DME on OCT with vision

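### Do the two visit terms in the primary composite, and the silence on findings at the withdrawal closeout, leave the primary event undefined?

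*Combined protocol and SAP*

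**What the plan says.** The primary outcome in Section 6.1 (repeated in 1.8F) is a composite with three timing rules:

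- Retinopathy worsening counts at a protocol visit. For a participant with one study eye the rule is 2-step worsening "in the study eye at a protocol visit. This scale only takes into account the retinopathy level of the study eye".
- OCT-based edema counts as "Development of central-involved DME on OCT with vision loss at the 2-year or 4-year visit".
- Treatment for proliferative retinopathy or macular edema counts whenever it happens.

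The eye-level composite among the secondary outcomes (1.8F and 6.4) words the worsening component differently: "retinopathy worsening on the ETDRS Retinopathy Severity Scale for Individual Eyes (see Table 2 in Section 6) at 2 years or 4 years".

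On visits, Section 3.1 states: "Each participant will have protocol specific follow-up visits scheduled at 2 years", and again at 4 years. Footnote c to the 4-year column of the schedule (1.8E) covers early termination of the parent trial: "If the PROMINENT trial ends before a participant reaches the 4 year visit, one final visit within 3 months of" that ending. Section 5.3 adds a different closeout: "Study participants who withdraw will be asked to have a final closeout visit at which the testing described for the protocol visits will be performed". On censoring, Section 6.3.1 says that participants not observed to meet "outcome criteria and who are lost to follow up will be censored at the time of the last completed" visit.

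Section 6 opens by describing itself as a summary and promises a detailed analysis plan before the study is complete.

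**The concern.** Two visit terms inside one composite suggest two rules, and the wider of them has no definition. Two consequences seem to follow.

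First, suppose a protocol visit means only the 2-year and 4-year visits. A participant who withdraws is then photographed and scanned at a closeout whose findings cannot be events, while 6.3.1 might still credit event-free time up to that visit. The participant would be carried as event-free to a visit that documented worsening.

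Second, suppose the term is wider. Worsening on photographs at a closeout would then count, but OCT edema with vision loss at the same visit would not. For a participant with one study eye, the primary outcome and the eye-level composite share the eye, the scale, the 2-step threshold, and the edema and treatment components. One finding could then be an event in one outcome and not in the other.

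At stake would be some lost primary events and a classification choice left open until after data have accrued.

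**Working it through.** **Reading the text.** Section 3.1 describes the 2-year and 4-year visits as protocol-specific, and 3.2 then lists the testing for each protocol visit. Section 5.3 borrows that testing for the withdrawal closeout, so it treats protocol visits as already established and the closeout as something separate. Footnote c is attached to the 4-year column, so the trial-end closeout most naturally fills the 4-year slot. On this reading 6.1, 1.8F and 6.4 agree, and the unilateral discrepancy disappears. The two consequences above also need opposite readings of the same term, so they cannot both apply. The first further requires a narrow reading for events and a broad one for the last completed visit. If the closeout is inside both lists or outside both, events and censoring match.

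**Inputs (Section 6.2).** Four-year event rates of 12% on placebo and 5% on active treatment, hazard ratio about 0.4, 15% exponential attrition over 4 years, 600 participants. Equal allocation (300 per arm) is an assumption, because the documents do not state the ratio.

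**Reproducing the plan's figure.** ln(0.95)/ln(0.88) = 0.401, matching the stated 0.4. The attrition hazard is a = −ln(0.85)/4 = 0.0406 per year. The placebo event hazard is h = −ln(0.88)/4 = 0.0320, and the active hazard is 0.4 × 0.0320 = 0.0128. The probability of an observed event, h/(h+a) × [1 − exp(−4(h+a))], is 0.1109 on placebo and 0.0460 on active treatment, mean 0.0785. Freedman's formula needs (1.96 + 0.8416)² × (1.4/0.6)² = 42.7 events, and 42.7/0.0785 = 544. The plan states 536, a difference of 1.5%, so the inputs are being used as the plan uses them.

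**Expected events at 600.** 300 × 0.1109 = 33.3 and 300 × 0.0460 = 13.8, total 47.1.

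**Early leavers.** The 4-year window opens at 3 years 10 months (3.833 years). 600 × [1 − exp(−0.0406 × 3.833)] = 86.5, of whom 46.8 leave before year 2 and 39.7 after. For 900 participants the total is 129.8.

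**Events first visible at a withdrawal closeout.** Suppose every leaver attends.

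- Leaving before year 2: n × ∫₀² a·e^(−at)·(1 − e^(−ht)) dt = n × {[1 − e^(−2a)] − a/(a+h) × [1 − e^(−2(a+h))]}. For placebo this is 300 × (0.0780 − 0.5597 × 0.1351) = 0.72; for active treatment, 0.29.
- Leaving between year 2 and 3.833, event-free at year 2: n × ∫ a·e^(−at)·(e^(−2h) − e^(−ht)) dt = 0.53 and 0.22.
- Totals: 1.25 placebo + 0.51 active = 1.77, or 3.75% of 47.1 (3.76% and 3.73% by arm before rounding).

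**Edema.** Section 6.2 gives about 3% over 4 years in the whole ACCORD cohort on color photographs. Used only as an illustration, the same integrals over 600 participants give 0.35 + 0.27 = 0.62 events.

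**Half attendance (an assumption).** About 43 participants, 0.9 retinopathy events and 0.3 edema events.

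**Power if all such retinopathy events were ignored.** Φ(√D × 0.6/1.4 − 1.96) at hazard ratio 0.40: D = 47.1 gives 83.7%; D = 45.3 gives 82.3%; at half attendance, D = 46.2 gives 83.0%.

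**The case for a change.** The best case for a change is that a primary event definition belongs in the protocol, and that an analysis plan written later would start from wording that differs between 6.1 and 6.4. The synonym reading is also not forced. Section 3.2 refers to a grid of testing by visit, and the grid in 1.8E includes a pre-treatment column. Section 3.1 calls the trial-end visit a closeout rather than the 4-year visit. Because recruitment runs until the parent trial completes enrollment, some later participants may have that closeout instead of a 4-year visit. Settling the list before outcome data are reviewed would remove any suspicion of a post hoc choice.

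Part of this stands. No passage gives the endpoint status of imaging at the withdrawal closeout, and none gives it for the pre-treatment visit.

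The step from there to a protocol change does not stand. Section 6.3.1 speaks of participants lost to follow-up, and 5.3 treats withdrawal separately, so nothing in the text says that a withdrawer is credited with time while the worsening is ignored. That mismatch has to be built by combining two readings. The obvious rewording, limiting imaging events to the 2-year, 4-year or closeout visit, would also do harm because it shuts out the pre-treatment visit, which has full study procedures. That matters for the retinopathy-only secondary outcome when worsening is imaged just before edema treatment. It matters even for the primary outcome when the treatment is for a non-diabetic indication, since 1.8D asks for imaging before first treatment whatever the reason. A protocol amendment would need IRB review under 8.2, for little gain.

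**Conclusion.** No change to the plan follows. The two visit terms are probably synonyms. The remaining gap, which visits can yield an imaging event, is one that analysts would ordinarily fill in the detailed analysis plan by using one visit list for events and for censoring.

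The effect of the withdrawal-closeout gap is at most about 1.8 of 47 retinopathy events per 600 participants, spread almost evenly by arm in relative terms, and about 1.4 percentage points of power. No direction of bias is shown.

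This rests on the rates and exponential attrition in Section 6.2, on equal allocation, and on full closeout attendance. The last is implausibly generous, since 6.2 describes the 15% as lost to follow-up. The figure is an upper bound for a second reason: part of the 12% and 5% was photocoagulation, which counts at any time. If the placebo rate is higher, as 6.2 allows, the count would rise. The share should move little, because it is nearly identical at 12% and 5%. The pre-treatment visit was not quantified. It barely touches the primary composite, because treatment for proliferative retinopathy or macular edema is itself an event.

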Level in the eye	Severity	Scale Step
10	DR absent	1
20	Microaneurysms only	2
35	Mild NPDR (hard exudates, soft exudates, and/or mild hemorrhage)	3
43	Moderate NPDR (mild intraretinal microvascular abnormalities or moderate hemorrhage)	4
47	Moderately severe NPDR (mild venous beading, moderate intraretinal microvascular abnormalities or severe hemorrhage)	5
53	Severe or very severe NPDR (moderate/severe venous beading, severe intraretinal microvascular abnormalities and/or very severe hemorrhage)	6
60, 61	Scars of photocoagulation for PDR (60) or mild PDR (61)	7
65	Moderate PDR	8
71, 75	High-Risk PDR	9
81, 85	High-Risk PDR with vitreous hemorrhage	10

590

591 **6.2 Sample Size Estimation**

592 Based on data from eyes with baseline retinopathy in the ACCORD study, it is anticipated that
 593 approximately 50% of PROMINENT study participants will have minimal to severe NPDR (levels
 594 20-53) in at least one eye. Among participants with minimal to severe NPDR in at least one eye,
 595 the percentage of patients with either a 3-step patient-level progression or photocoagulation was
 596 approximately 5% in the fenofibrate group and 12% in the placebo group. For the entire ACCORD
 597 cohort (i.e. with and without baseline retinopathy), the rate of DME worsening on color
 598 photographs was approximately 3% over 4 years in both the fenofibrate and control groups.
 599 However, the percentage of patients with baseline retinopathy and worsening DME without
 600 worsening retinopathy is not reported. In addition, DME progression in ACCORD was assessed by
 601 color photographs while in the current study it will be assessed by OCT, which has been shown to
 602 be more sensitive at detecting DME.³² Therefore, it is unknown what impact the primary outcome
 603 components, besides retinopathy progression, will have on the projected outcome, resulting in
 604 uncertainty around these estimates.

605

606 The table below shows the required sample size for 80% power with a type I error rate of 5% and a
 607 null hypothesis of no difference between groups (two-tailed test) for a time-to-event outcome (log-
 608 rank test). These calculations were based on the 4-year outcome rate in the placebo group and the
 609 resulting hazard ratio when comparing the outcome rate in the pemafibrate group. The outcome
 610 times are assumed to follow an exponential distribution and the estimates include adjustment for

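### Section 6.2 calls its power estimates conservative, but the added treatment and DME events could lower power as well as raise it, and the ACCORD 12% is described in two ways

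*Combined protocol and SAP*

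**What the plan says.** All of this is in section 6.2 (Sample Size Estimation).

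- **What the ACCORD rates count.** Among participants with minimal to severe NPDR, "the percentage of patients with either a 3-step patient-level progression or photocoagulation was" about 5% on fenofibrate and 12% on placebo.
- **What is known about DME.** In the whole ACCORD cohort, DME worsening on color "photographs was approximately 3% over 4 years in both the fenofibrate and control groups". The section adds a caveat: "However, the percentage of patients with baseline retinopathy and worsening DME without" worsening retinopathy is not reported. It concludes: "Therefore, it is unknown what impact the primary outcome" components other than retinopathy progression will have.
- **The sample size.** The 5% and 12% "yield a hazard ratio of approximately 0.4, resulting in a required sample size of 536 participants".
- **The later description of the 12%.** After the detectable hazard ratios for 600 participants, the 12% is said to cover events "due only to progression of retinopathy on photographs and does not include treatment-related and" DME-related events, so the placebo rate could exceed 16%.
- **The inference.** If outcome rates in "the placebo group are higher than projected, the study will be powered to detect smaller reductions" "in the hazard of diabetic retinopathy worsening. Therefore, the estimates given here are" conservative.

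The primary outcome in section 6.1 is the full composite: retinopathy worsening, a procedure for PDR, treatment for DME, or central-involved DME on OCT with vision loss.

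**The concern.** There are two faults.

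First, the two descriptions of the 12% do not agree. Photocoagulation is a treatment, and section 6.1 lists PRP among the treatment components of the composite. The later text uses the supposed absence of treatment events as its reason to expect a higher placebo rate, so the description carries part of the argument.

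Second, the argument looks only at the placebo rate. Log-rank power depends on the number of events and on the composite hazard ratio. Extra events add information, but if the drug affects them less than it affects retinopathy they also pull the composite hazard ratio towards 1. The net effect can go either way. The section first calls the impact unknown and then gives it a favorable direction.

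At stake is how the 80% power claim is read. A reader told that the estimates err on the safe side could take a null composite result as stronger evidence against a retinopathy benefit than the design supports. Recruitment runs until the parent trial closes enrollment, up to 900, so no sample-size decision depends on this.

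**Working it through.** **Inputs from section 6.2:** two-sided 5% log-rank test, 80% power, exponential event times, 15% exponential attrition over 4 years, 4-year rates of 12% and 5%, 600 participants. The cap of 900 is in section 2.1. **Assumed:** 1:1 allocation, because section 6.2 gives no ratio.

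**Formulas.** With 4-year cumulative event hazard h and attrition hazard c = −ln(0.85) = 0.1625, the probability of an observed event is p(h) = h/(h+c) × [1 − exp(−(h+c))]. Expected events are d = N × (mean of p over the two arms). Freedman power = Φ(√d × (1−HR)/(1+HR) − 1.96).

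**Step 1: reproduce the plan.**
- HR = ln(0.95)/ln(0.88) = 0.0513/0.1278 = 0.401.
- Events needed at HR 0.40: (1.96+0.8416)² × (1.4/0.6)² = 42.7, which gives N = 544 against the stated 536.
- All 15 cells of Table 3 agree within 3%. An expected log-rank calculation gives 536 and matches every cell within 3 participants.
- Detectable HR at 600 is 0.490 for a 16% placebo rate and 0.319 for 8%, against the stated 0.49 and 0.32.

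The stated arithmetic is sound.

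**Step 2: power for the ACCORD endpoint alone.** p = 0.1109 and 0.0462, so d = 600 × 0.0786 = 47. Power = Φ(6.87 × 0.427 − 1.96) = 83.5% at 600, and 94.9% at 900.

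**Step 3: add a separate DME component of 3%.** Its cumulative hazard is −ln(0.97) = 0.0305. The rate comes from the plan, but applying it here without overlap is an assumption. With no drug effect on DME:
- Composite HR = (0.0513+0.0305)/(0.1278+0.0305) = 0.516.
- Rates are 1 − 0.88×0.97 = 14.6% and 1 − 0.95×0.97 = 7.9%.
- d = 600 × 0.104 = 62, and power = Φ(7.90 × 0.319 − 1.96) = 71.2%.

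| Added to 12% v 5% | Composite HR | Power at 600 | Power at 900 |
|---|---|---|---|
| Nothing | 0.401 | 83.5% | 94.9% |
| 3% DME, HR 1 | 0.516 | 71.2% | 87.0% |
| 3% DME, HR 0.69 | 0.457 | 82.3% | 94.2% |
| 3% DME, HR 0.40 | 0.401 | 90.1% | 97.8% |

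The 0.69 is FIELD's hazard ratio for first laser treatment (section 1.4). It pools DR and DME, so it only illustrates. The expected log-rank calculation gives 84.2% for the first row and 71.9% for the second at 600, with 731 participants needed for 80% power in the second.

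**Step 4: where the direction changes.** With 3% DME as the only addition, power at 600 falls below 83.5% once the DME hazard ratio exceeds about 0.65, and below 80% once it exceeds about 0.76.

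**Step 5: less severe variants, neutral DME, N = 600.**
- Half of the DME events overlapping with retinopathy events (13.5% v 6.5%): 78.0%.
- Three-quarters overlapping (12.75% v 5.75%): 80.7%.
- No overlap, plus 1, 2 or 3 points of PDR-treatment events at HR 0.40: 75.0%, 78.5% or 81.5%.

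**Step 6: the detectable effect.** At 600 and 80% power, 3% neutral DME eases the detectable composite HR from 0.42 to 0.47. The retinopathy HR needed to produce it is (0.470×0.1583 − 0.0305)/0.1278 = 0.34, a larger reduction than 0.42. At a DME HR of 0.69 it stays at 0.42, and at 0.56 (the lower limit of the FIELD interval) it eases to 0.45.

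**Step 7: the plan's own table.** Table 3 asks for 536 participants at 12% and HR 0.40, but 618 at 16% and HR 0.50. A higher placebo rate with a weaker effect needs more participants.

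**The case against.** The sentence about detecting smaller reductions is true at a fixed power: a higher placebo rate does ease the detectable composite hazard ratio. If the estimates in question are only required numbers at a given hazard ratio, calling them conservative can be defended. The protocol also tends to use retinopathy worsening as shorthand for the composite (the primary objective in section 1.7 does), and on that reading step 6 loses its force. The uncertainty is disclosed earlier in section 6.2, and Table 3 shows what a hazard ratio of 0.50 would need. The Tables 1 and 2 of section 6.1 grade PRP or photocoagulation scars as severity steps, so part of the mismatch over the 12% may be terminology. Finally, 71% is an unfavorable corner: no drug effect on DME, no overlap, no added PDR-treatment events, and a 3% rate from a different population and a different measurement.

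Most of this stands, and it limits the size of the point. It does not rescue the inference. The 12% and 5% are used to set the hazard ratio of 0.4 for the primary composite, and the conclusion is offered as reassurance about the power of that analysis. It is safe only if the composite hazard ratio stays near 0.4 when the other components are added, and nothing in the plan supports that. The only DME figure given shows no difference between arms. Disclosing the uncertainty and then assigning it a direction is the inconsistency. Even if the 12% mismatch is terminology, the section lists photocoagulation separately in one place and excludes treatment events in another.

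**Conclusion.** The concern holds. The sample sizes and detectable hazard ratios are calculated correctly, but the claim that they are conservative is not supported. Power for the composite may be above or below that for the ACCORD retinopathy endpoint alone. With 3% of separate DME events at 600 participants it runs from 71% (no drug effect on DME) to 90% (the same effect as on retinopathy), against 83.5% without them; at 900 the range is 87% to 98%. These figures assume 1:1 allocation, exponential times, 12% and 5% for retinopathy events, and component rates, overlap and effects that the plan does not give. They show that the direction is undetermined, not that the trial falls short. The two descriptions of the 12% also need to be aligned. The point should be fixed because the section states a property of the power that its own figures do not establish.

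**What to change.** In section 6.2:

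1. Describe the ACCORD 12% and 5% the same way throughout, as 3-step progression or photocoagulation, excluding other treatments and DME.
2. Delete the statement that the estimates are conservative. Say instead that power for the composite may be higher or lower than for retinopathy events alone, depending on how far the drug affects the added events.
3. State that the hazard ratio of 0.4 and the 536 participants rest on progression or photocoagulation only.
4. Add two scenarios labeled as assumptions: 3% separate DME with no drug effect (71% at 600, 87% at 900) beside 3% with a hazard ratio of 0.40 (90% and 98%). A fuller grid over rate, overlap and effect is optional.

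The cost is a few sentences and a slightly less favorable power statement. No extra participants are needed, and the endpoint and analysis stay as they are.
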